3.6 Definition

Term	Unit of measurement	Severe	Moderate	Mild	General
	Hemoglobin concentration (g/L)	< 70.0	>= 70.0 to < 100.0	>=100.0 to < 120.0	< 120.0
Anemia (infants)	Hemoglobin concentration (g/L)	< 70.0	>= 70.0 to < 90.0	>= 90.0 to < 100.0	< 100.0
Under- weight	Weight-for-age z-score (WHO 2006)	< -3	>= -3 to < -2	>= -2 to < -1	< -2
Stunting	Length-for-age z-score (WHO 2006)	< -3	>= -3 to < -2	>= -2 to < -1	< -2
Wasting	Weight-for-length z-score (WHO 2006)	< -3	>= -3 to < -2	>= -2 to < -1	< -2
Low MUAC for age	MUAC-for-age z-score (WHO 2006)	< -3	>= -3 to < -2	>= -2 to < -1	< -2
	Head circumference-forage z-score (WHO 2006)	< -3	>= -3 to < -2	>= -2 to < -1	< -2

4.0 Statistical analysis

4.1 Study flowchart

A participant flow diagram will be prepared in accordance with the CONSORT 2010 guidelines (**Figure 1**).

4.2 Procedures for data cleaning

We performed data cleaning at various points during data collection:

- a. At the field site, data monitors manually checked all forms for completeness and consistency, and resolved queries before forms were sent to Accra for double entry by two different data entry clerks.
- b. At the Accra office, the data manager verified and/or compared the entries by the two entry clerks. Differences between the entries were resolved by re-checking the original (scanned) forms before a common dataset was generated.
- c. In Accra, queries generated from the common dataset using special SAS and Stata syntax written by project managers were forwarded to the field office and resolved by rechecking

the original data form (including obtaining clarification from the field worker who completed the form), or by a repeat home visit whenever possible.

4.3 Outliers

- We will check outliers by visually inspecting Box plots and/or histograms of individual continuous variables, and scatterplots of related variables.
- Outliers which are clearly impossible or implausible values will be corrected if possible, or recoded to missing if correction is not possible.
- Outliers which are plausible or possible will be kept. In analysis of secondary outcomes, variables with outliers will be transformed, and in an extreme situation, a sensitivity analysis will be done to determine if such outliers have undue influence on the results.

4.4 Software

All analyses will be done using SAS version 9.3 (SAS Inst. Cary, NC, USA) or Stata version 10.1 or higher (StataCorp, TX, USA). The WHO 2006 Child Growth Standards will be used for age-and-sex standardization of child weight, length, head circumference, arm circumference and weight-for-height.

4.5 Background characteristics of participants and baseline comparisons

For all variables measured (with the exception of some particular socio-economic status variables), the available values at the time of screening, recruitment or enrolment, prior to the first intake of the study supplement will be considered as background or baseline characteristics. The background characteristics of subjects who completed the study will be presented in a table, by treatment group. **Table 1a** will be used in analysis involving women, and **Table 1b** in analysis involving infants. However, for specific papers, only selected background characteristics considered relevant to those papers will be presented.

Analysis of background characteristics will be completed as follows:

- We will use frequencies and percentages to summarize categorical data. Percentages will be calculated based on the number of participants for whom data are available.
- Continuous variables will be summarized using either mean and SD for variables, or median and range.
- Where data for certain participants are missing, the number of participants included in the analysis will be indicated.

4.6 Potential effect modifiers

The following variables will be considered as effect modifiers:

- a. Baseline value for the outcome being analyzed (with the exception of birth outcomes, where baseline values are not possible)
- b. Proxy variable for household food insecurity
- c. Proxy variable for household socio-economic status or wealth
- d. Parity or order of pregnancy
- e. Maternal height

- f. Maternal BMI at enrolment (adjusted for gestational age)
- g. Maternal anemia at enrolment
- h. Gestational age at enrolment
- i. Season at enrollment
- j. Maternal age
- k. Maternal education
- 1. Sex of child (in analyses involving children)
- m. One or several proxy indicators for diet quality

The specific effect modifiers that will be considered in each analysis have been indicated in the sections below.

4.7 Timing of measurement of outcome variables

The outcome variables were measured after enrolled women had started taking the study supplements. The table below shows the timing of measurement of the outcome variables.

i. Women

Variable	Measurement	
Morbidity and supplement	Measured every two weeks (± 7 days) after enrolment	
intake	(beginning of supplement intake) until 6 months (± 1 month)	
	post-partum.	
Food Frequency and	Measured at 36 gestational weeks and 6 months post-partum.	
anthropometric and blood	In practice, measurement at 36 gestational weeks occurred	
indices	when woman was at least 36 gestational weeks and had not	
	yet delivered. Measurement was considered missed after	
	woman had delivered.	
	Measurement at 6 months post-partum occurred within one	
	month of turning 6 months post-partum.	
Urinary indices	Measured at 36 gestational weeks. In practice, measurement	
	occurred when woman was at least 36 gestational weeks and	
	had not yet delivered. Measurement was considered missed	
	after woman had delivered.	
Saliva indices	Measured at 28 and 36 gestational weeks. In practice,	
	measurement at the 28 gestational weeks occurred within two	
	weeks of reaching 28 weeks. The measurement at 36	
	gestational weeks occurred when woman was at least 36	
	gestational weeks, and had not yet delivered, and was	
	considered missed after woman had delivered.	

ii. Infants

Variable	Measurement
Morbidity and supplement	Measured weekly (±3 days) during home visits from birth to
intake	completed 18 months of age.
Food frequency at 0-5 months	Measured within one week of child's monthly anniversary

Variable	Measurement
of age	from 0 to 5 months of age.
Food frequency at 6, 9, 12, 15	Measured within one week of turning 6, 9, 12, 15 and 18
and 18 months of age	months of age.
-	Measured within 48 hours after birth, and at 3, 6, 12 and 18 completed months of age.
Blood indices	Measured within three weeks of turning 6 months of age, and
	also at 18 completed months of age.

4.8 Analysis of the effect of the intervention

The analysis of the effect of the intervention (at single time points or repeated measures) will begin with testing the null hypothesis of no difference among the three treatment groups using ANCOVA or logistic regression, and controlling for pre-specified covariates including, in the case of women, baseline values. Because infants will not have true baseline values unaffected by intervention, most of the covariates used in analyses involving infants will be mothers' baseline characteristics. Only covariates significantly associated with an outcome at 10% level of significance in a bivariate analysis will be include in the final adjusted analysis. This means we may have different sets of covariates for each outcome.

For all analyses, if the global null hypothesis is rejected at 0.05 level, then we will perform post-hoc pairwise comparisons of all three groups using Tukey-Kramer adjustment (for continuous variables) or the "Contrast" statements (for categorical variables) in SAS. We will also use Scheffe's test to assess whether the LNS group differs from the non-LNS groups with respect to most outcomes, and whether the IFA group differs from the non-IFA groups with respect to iron outcomes or variables such as morbidity which might be affected by iron status.

The effects of potential effect modifiers will be assessed with an interaction term in the ANCOVA or logistic regression model. Significant interactions (p < 0.05) will be further examined with stratified analyses, estimation of separate regression lines, or estimation of adjusted means at key points of the covariate, in order to understand the nature of the effect modification.

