2.8 Safety outcomes

We assessed safety by evaluating (a) Adverse events (b) Severe adverse events, and (c) Abnormally low anthropometric values.

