2.8.2 Serious adverse events

Serious adverse events (SAE) outcomes:

- a) Number of SAEs reported, ie. if a subject has more than one occurrence of SAEs, all the SAEs will be counted.
- b) Number and proportion of subjects with SAEs i.e. if a subject has more than one occurrence of SAEs, the subject will be counted only once.

Conditions regarded as SAEs were:

- a. Death of subject.
- b. Any loss of pregnancy regardless of gestational age.
- c. Hospitalization (overnight stay in the hospital because of illness).
- d. Hemoglobin less than 5.0 g/dl (or 50 g/l).
- e. Subject extremely ill. This is used to define (a) "life-threatening conditions" (including seizures, coma, tetany, diabetic ketoacidosis, disseminated intravascular coagulation, diffuse petechiae, paralysis, acute psychosis, severe depression), (b) "persistent or significant disability / incapacity" and (c) "other serious medical condition".
- f. Congenital abnormality/ birth defect.

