2.9 Analysis principles

- The primary analysis will be by intention-to-treat. That is, results for all women enrolled (including data on their infants) will be analyzed according to the group to which they were assigned regardless of any protocol violations. Data on subjects who were lost to follow-up because of death, travel from the study site, or refusal to continue with the study will be included in the analysis if available.
- All tests will be two-sided, at 5% level of significance.
- Where more than 10% of observations are missing for a dependent variable, we will report the number of observations used in the analysis.

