3.0 Design

3.1 Sample size and power

Sample size calculations were based on being able to detect an effect size of 0.3 (difference between groups, divided by the pooled SD) for each outcome, assuming 3 groups, power of 80% and alpha=0.05. This required 216 per group, for a total of 648 subjects. Allowing for up to 25% loss to follow-up by 18 months, we needed to recruit 864 subjects. For the biochemical outcomes, we assumed an effect size of at least 0.5, which required a subsample of 79 per group, for a total of 315 subjects after allowing for attrition.

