4.14 Confidence intervals

Estimates of treatment effects will be accompanied by a 95 % confidence interval, wherever possible.

Tables

Table 1aBaseline characteristics of women who completed the study

Variable	IFA $(\bar{x} \pm SD)[n]$	$\frac{\mathbf{MMN}}{(\bar{x} \pm \mathbf{SD})[\mathbf{n}]}$	LNS $(\bar{x} \pm SD) [n]$	P- value	Test
Number of participants	X.X	X.X	X.X		
Age, y	$x.x \pm x.x [x]$	$x.x \pm x.x [x]$	$x.x \pm x.x [x]$	x.xx	ANOVA
Years of formal education	$x.x \pm x.x [x]$	$x.x \pm x.x [x]$	$x.x \pm x.x [x]$	x.xx	ANOVA
Marital status (% [n])	x.x [x]	x.x [x]	x.x [x]	X.XX	Chisq
Proxy for socioeconomic status	$x.x \pm x.x [x]$	$x.x \pm x.x [x]$	$x.x \pm x.x [x]$	X.XX	ANOVA
Parity	$x.x \pm x.x [x]$	$x.x \pm x.x [x]$	$x.x \pm x.x [x]$	X.XX	ANOVA
Weight (kg)	$x.x \pm x.x [x]$	$x.x \pm x.x [x]$	$x.x \pm x.x [x]$	X.XX	ANOVA
Height (m)	$x.x \pm x.x [x]$	$x.x \pm x.x [x]$	$x.x \pm x.x [x]$	X.XX	ANOVA
BMI (kg/m ²)	$x.x \pm x.x [x]$	$x.x \pm x.x [x]$	$x.x \pm x.x [x]$	X.XX	ANOVA
Mid upper arm circumf. (cm)	$x.x \pm x.x [x]$	$x.x \pm x.x [x]$	$x.x \pm x.x [x]$	X.XX	ANOVA
Triceps skinfold (cm)	$x.x \pm x.x [x]$	$x.x \pm x.x [x]$	$x.x \pm x.x [x]$	X.XX	ANOVA
Gestational age at enrolment	$x.x \pm x.x [x]$	$x.x \pm x.x [x]$	$x.x \pm x.x [x]$	X.XX	ANOVA
Hemoglobin	$x.x \pm x.x [x]$	$x.x \pm x.x [x]$	$x.x \pm x.x [x]$	X.XX	ANOVA
Positive rapid test for malaria (%)	x.x [x]	x.x [x]	x.x [x]	X.XX	Chisq
Elevated Acute phase response (%)	x.x [x]	x.x [x]	x.x [x]	X.XX	Chisq
ZPP	$x.x \pm x.x [x]$	$x.x \pm x.x [x]$	$x.x \pm x.x [x]$	X.XX	ANOVA
TfR	$x.x \pm x.x [x]$	$x.x \pm x.x [x]$	$x.x \pm x.x [x]$	X.XX	ANOVA
Ferritin (geometric mean)	$x.x \pm x.x [x]$	$x.x \pm x.x [x]$	$x.x \pm x.x [x]$	X.XX	ANOVA
Anemia (%)	xxx/ xxx (xx)	xxx/ xxx (xx)	xxx/ xxx (xx)	X.XX	Chisq
Plasma lipid profile	$x.x \pm x.x [x]$	$x.x \pm x.x [x]$	$x.x \pm x.x [x]$	X.XX	Chisq

Table 1bBaseline characteristics of infants who completed the study

Variable	IFA	MMN	LNS	P-	Test
	$(\bar{x} \pm SD) [n]$	$(\bar{x} \pm SD)[n]$	$(\bar{x} \pm SD)[n]$	value	
Number of participants	x.x	X.X	X.X		
Mother's education (y)	$x.x \pm x.x [x]$	$x.x \pm x.x [x]$	$x.x \pm x.x [x]$	x.xx	ANOVA
Mother's marital status (% [n])	x.x [x]	x.x [x]	x.x [x]	x.xx	Chisq
Number of persons in the household	x.x ± x.x [x]	$x.x \pm x.x [x]$	$x.x \pm x.x [x]$		Kruskal Wallis
Children <5 y in the household	x.x ± x.x [x]	$x.x \pm x.x [x]$	$x.x \pm x.x [x]$		Kruskal Wallis

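### Section 4.8 makes arm-versus-arm comparisons conditional on a significant three-group test without exempting safety, and no other section fixes such an estimate for serious adverse events

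*SAP*

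**What the plan says.** Section 2.8 makes safety a formal part of the evaluation: "We assessed safety by evaluating (a) Adverse events (b) Severe adverse events, and (c) Abnormally low anthropometric values". Section 2.8.2 lists the serious adverse events (SAEs), which include death, any loss of pregnancy, overnight hospitalization and congenital abnormality. It defines two measures: the number of SAEs, and "Number and proportion of subjects with SAEs i.e. if a subject has more than one occurrence of SAEs, the subject will be counted only once". Section 2.8.3 adds wasting and severe wasting at 3, 6, 12 and 18 months. None of these subsections names a comparison between arms.

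The general rule is in section 4.8. The analysis of the intervention begins with "testing the null hypothesis of no difference among the three treatment groups using ANCOVA or logistic regression", and then: "For all analyses, if the global null hypothesis is rejected at 0.05 level, then we will perform post-hoc pairwise comparisons of all three groups". Section 2.9 sets the level: "All tests will be two-sided, at 5% level of significance". Section 4.8 also plans Scheffe contrasts of LNS against the two other arms for most outcomes, and of IFA against the two other arms for iron outcomes and variables such as morbidity.

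Three places provide estimates without this condition:

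- Section 4.10 summarizes categorical secondary outcomes at single time points with odds ratios and 95% intervals.
- Table 4 lays out adjusted odds ratios for underweight, stunting and wasting at 18 months.
- Section 4.14 says: "Estimates of treatment effects will be accompanied by a 95 % confidence interval, wherever possible".

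No table shell covers adverse events or SAEs.

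**The concern.** A global test before pairwise comparisons guards against false claims of efficacy. For harm, the costlier error is to miss an excess, and the useful result is an interval whose upper limit shows how much excess risk the data still permit. Section 4.8 makes no such distinction. For a rare SAE the likely output is three counts and one non-significant p-value, with no LNS-IFA, MMN-IFA or LNS-MMN estimate that the plan requires. The trial was sized for a 0.3 SD difference in continuous outcomes, so that p-value would carry little information about rare harm.

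**Working it through.** **1. The plan's own figure.** Section 3.1 assumes an effect size of 0.3, "assuming 3 groups, power of 80% and alpha=0.05", and says "This required 216 per group, for a total of 648 subjects". A one-way F test on three groups with means 0, d/2 and d has noncentrality n·d²/2 = 216 × 0.045 = 9.72. With 2 and 645 degrees of freedom this gives power 0.802, so 216 per group is reproduced. Then 648/0.75 = 864, or 288 per arm if allocation is equal. The calculation concerns continuous outcomes; section 3.1 contains none for event risks.

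**2. Which sections reach the SAEs.**

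| Section | What it provides | Does it fix an arm-versus-arm SAE estimate? |
|---|---|---|
| 2.8.2 | Counts and proportions of subjects | No |
| 4.8, pairwise | All pairs, if the global test is significant | Only on that condition |
| 4.8, Scheffe | One arm against the other two | No, the other arms are combined |
| 4.10 | Odds ratios for categorical secondary outcomes | No; section 2.7.2 lists morbidity but not deaths, pregnancy losses, hospitalizations or birth defects |
| 4.14 | An interval for each estimate that is made | No; it does not say which estimates are made |
| Table 4 | Odds ratios for malnutrition at 18 months | No |

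Table 4 shows odds ratios under IFA and MMN and none under LNS. LNS is thus apparently the reference, and no MMN-IFA estimate appears there either. Wasting at 3, 6 and 12 months is outside it.

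**3. How often the global test would be significant.** Inputs: 288 per arm (864/3) or 216 per arm (the 18-month size), and risks p, p and 2p. The test is a Pearson chi-square on 2 degrees of freedom with critical value 5.99. The SAP gives no event rates, so p is an assumption shown over a range. The results come from simulation, 100,000 trials per scenario:

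| Base risk p | 288 per arm | 216 per arm |
|---|---|---|
| 1% | 17% | 13% |
| 2% | 31% | 24% |
| 3% | 44% | 35% |
| 5% | 68% | 55% |
| 10% | 95% | 88% |

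With a doubled risk, the condition fails more often than not up to a base risk of about 3% (288 per arm) or 4% (216 per arm), but not for commoner events.

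**4. Is the condition the cause of the low power?** Mostly not. A single unconditional pairwise test at 5% with 288 per arm has power 16.5%, 29% and 62.5% at base risks of 1%, 2% and 5%, against 17%, 31% and 68% for the global test. Reaching 80% on the global test would need about 1905, 940 and 360 per arm.

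**5. What an interval adds.** Take 9, 9 and 17 events (IFA, MMN, LNS) among 288 per arm.

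- Expected events per arm: 35/3 = 11.667. Pooled risk: 35/864 = 0.0405.
- Chi-square = (2 × 2.667² + 5.333²) / (11.667 × 0.9595) = 42.67/11.19 = 3.81, so p = 0.149. Section 4.8 stops here.
- LNS versus IFA: RR = 17/9 = 1.89. SE of log RR = √(1/9 + 1/17 − 2/288) = 0.404.
- 95% CI = 1.89 × exp(±1.96 × 0.404) = 0.86 to 4.17.

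The interval includes 1, so it establishes no harm. It also does not exclude a fourfold risk, and the global p-value does not show that.

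**The case against.** The strongest reply is that section 4.8 restricts post-hoc tests, not estimates, and that the plan gives unconditional estimates elsewhere. Much of this stands. A reader might infer that no arm-versus-arm safety estimate will be made at all. The document does not support that: Table 4 covers wasting and severe wasting at 18 months, and section 4.10 covers morbidity where it is analysed as a categorical secondary outcome. The gap is confined to SAEs and the other safety outcomes that those two places do not reach.

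A reader might also infer that a non-significant test will be reported as showing no difference. The SAP does not say so anywhere. It leaves that reading open and does nothing to prevent it.

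It can be argued that section 4.8 was never meant for SAEs, since section 2.8.2 reads as descriptive and a count with repeat events fits neither ANCOVA nor logistic regression. That is possible, as section 4.8 does not mention safety. But the rule as worded covers every analysis, and the clarification needed is the same on either reading.

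The Scheffe contrasts are not stated to depend on the global test. For continuous outcomes, however, such a contrast cannot be significant unless the global F test is. Section 3.5 lets the monitoring board or the ethics board request morbidity and mortality by group, but that concerns interim review, not final reporting.

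Finally, the low detection rates reflect sample size, and SAEs pooled over all categories may not be rare. Both points are accepted.

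**Conclusion.** The point holds as a gap in safety reporting that is cheap to close. Section 4.8 applies an efficacy-type condition to every analysis without exempting safety, and for SAEs nothing else in the SAP fixes a pairwise estimate. With 288 per arm and a doubled risk in one arm, about 83%, 69% and 56% of trials would stop at the global test at base risks of 1%, 2% and 3%, falling to 32% at 5% and 5% at 10%. These figures assume equal allocation, a Pearson chi-square as the global test, and event rates that the SAP does not give.

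They describe how often no pairwise result would follow. They do not measure power lost through the condition, because removing it leaves the power of any single comparison about the same. The benefit of a change is a visible upper confidence limit.

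**What to change.** In section 4.8, keep the global test as the condition for efficacy comparisons and exempt the safety outcomes of section 2.8. For each SAE category (death, pregnancy loss, hospitalization, congenital abnormality and the others listed), for subjects with any SAE, and for wasting and severe wasting at each age, always report LNS-IFA, MMN-IFA and LNS-MMN. Give each as a risk difference or risk ratio with a 95% confidence interval, exact or score-based where events are few. Label these intervals descriptive and unadjusted for multiplicity. State that a non-significant global test is not taken as evidence of no harm.

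The cost is a few sentences and one added safety table, with no new data. The small downside is that some unadjusted intervals will exclude no effect by chance: with three unconditional 5% comparisons on one outcome, about 12% of trials with no true difference show at least one. The descriptive label addresses this.

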3.3 Treatment groups

Study participants who completed baseline anthropometric and laboratory assessments were randomized into three groups using block randomization, to ensure even distribution of groups across time. Sealed, opaque envelopes bearing the group designations were prepared (by Study Statistician) and arranged in groups (Blocks), each block containing nine envelopes. There were 96 blocks in all, numbered block #1 to block #96, hence a total of 864 (96 x 9) envelopes. For each woman being randomized, the Study Nurse doing the randomization took the topmost 9 envelopes (i.e. starting with block #1), shuffled the nine envelopes in the block, and then offered the woman a choice of any of the nine. After woman made a pick, Nurse returned the remaining eight envelopes to the top of the pile. This process of presenting nine envelopes at a time for each woman to make a pick continued until there were less than nine envelopes left in the whole pile (block #96).

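### With three groups, Tukey-Kramer behind a significant global test is a second adjustment that familywise control does not need; at 216 per group it costs about 3 to 13 points of pairwise power

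*SAP*

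**What the plan says.** SAP section 3.1 sizes the trial to "detect an effect size of 0.3 (difference between groups, divided by the pooled SD"), "assuming 3 groups, power of 80% and alpha=0.05". The result is stated as "This required 216 per group, for a total of 648 subjects", and then "Allowing for up to 25% loss to follow-up by 18 months, we needed to recruit 864 subjects". The section does not say whether the 80% belongs to the global three-group test or to a comparison of two groups, and it does not place the third mean.

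Section 4.8 begins with a global ANCOVA or logistic regression test of the three groups. Then, "if the global null hypothesis is rejected at 0.05 level, then we will perform post-hoc pairwise comparisons of all three groups using Tukey-Kramer adjustment". That step covers the continuous outcomes; for categorical ones it names SAS CONTRAST statements and does not say whether their p-values are adjusted. It adds a Scheffé test of LNS against the non-LNS groups for most outcomes. Section 2.9 sets the level: "All tests will be two-sided, at 5% level of significance".

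In Tables 2 and 3 each outcome has a single p-value column labelled ANCOVA.

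**The concern.** The global gate and Tukey-Kramer each guard against the same thing, a false pairwise claim among three groups. Requiring both makes the rule stricter than the 5% level that the plan sets itself. The price is power for the statements readers will look for, namely which supplement differs from which. Null hypothesis (b) in section 2.5 sets LNS infants against those of the other two groups, so the natural claim is that LNS differs from IFA and from MMN, and this is where the loss is largest.

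A second consequence is one of reading. Section 3.1 describes its effect size as a difference between groups, so the 80% may be taken as the power to declare such a difference under the rule in 4.8. The SAP gives no power for that rule.

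**Working it through.** **Inputs.** From 3.1: 0.3 SD, three groups, alpha 0.05, 80% power, 216 per group. From 2.9: two-sided tests. From 4.8: the two-step rule. Equal allocation follows from 216 per group. The position of the third mean is not given and is assumed below.

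**1. Reproduce 216.** Take a one-way F-test with means (0, 0.15, 0.30) SD. The noncentrality is λ = n × Σ(mean − grand mean)² = 216 × (0.15² + 0 + 0.15²) = 216 × 0.045 = 9.72. With 2 and 3 × 215 = 645 degrees of freedom, power is 80.2%, and 216 is the smallest n that reaches 80%. The same method at 0.5 SD gives the 79 per group that 3.1 states for biochemical outcomes. Other methods do not give 216: a two-sample comparison at 5% needs 175; Bonferroni needs 212 (two comparisons) or 233 (three); the F-test with the third mean at an extreme needs 162. Also 648 / 0.75 = 864. So 216 is the size for the global test with the third mean midway.

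**2. Critical values on 645 df.** Tukey: q(0.05; 3, 645) / √2 = 2.349. Unadjusted t: 1.964. For a 0.3 SD pair the noncentrality is 0.3 × √(216/2) = 3.118.

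**3. Power at 216 per group, no covariates.** The joint events (F significant and pair significant) were simulated with at least one million trials per setting.

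| Means and claim | F, then Tukey | F, then unadjusted t |
|---|---|---|
| (0, 0.15, 0.30): extreme pair | 76.7% | 79.4% |
| (0, 0, 0.30): LNS against one given arm | 77.6% | 84.9% |
| (0, 0, 0.30): LNS against both arms | 65.9% | 79.1% |

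The differences are 2.7, 7.3 and 13.2 points. Tukey-Kramer without the gate gives 77.9% for a 0.3 SD pair, so the gate itself costs 77.9 − 76.7 = 1.2 points in the first row and 77.9 − 77.6 = 0.3 in the second.

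**4. Familywise error.** If all three means are equal, no pairwise claim can be made unless the F-test rejects, which happens 5% of the time. If exactly two are equal, there is one true pairwise null, tested at 5%. No other case contains a true pairwise null. The gate with unadjusted tests therefore controls the familywise error at 5%; this short argument works for three groups and not for four or more. Simulated error is 5.0% under the full and partial nulls. The planned rule gives 4.5% under the full null and 1.9% when LNS stands apart from two equal groups.

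**5. The Scheffé contrast.** With LNS 0.3 SD above two equal groups, the contrast has standard error √(1/216 + 1/432) = 0.0833 SD and noncentrality 0.3 / 0.0833 = 3.6. The critical value is √(2 × 3.01) = 2.45, where 3.01 is the F critical value. Power is 87.4%.

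**The case against.** The strongest reply is that nothing in the plan is invalid. Section 3.1 never says that the 80% is pairwise. The global test is the first step in 4.8, it is the only test with a p-value in Tables 2 and 3, and it matches null hypothesis (a). Tukey-Kramer is a standard choice, and a gate in front of it makes it conservative, not wrong. All of this stands. A reader might infer that the trial was mis-sized or has less power than claimed; the documents do not support that, because 216 and 80% are exact for the global test.

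The plan also has its own test for the case where LNS stands apart, the Scheffé contrast, with 87.4% power. That stands too, and it means that a distinct LNS effect would not go undetected. But the contrast compares LNS with the average of the other arms and cannot support a claim against each of them.

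The 76.7% is an unfavourable case. The primary analysis is ANCOVA. The SAP gives no R-squared; if the covariates explain 5%, 7% or 10% of the variance, planned-rule power becomes 79.1%, 80.1% or 81.5%. The 25% loss applies by 18 months, while birth length is measured within 48 hours of delivery. The SAP gives no loss figure at birth; with 864 / 3 = 288 randomised per group, planned-rule power is about 80% at 230 measured (20% loss), 85% at 259 (10%) and 89% at 288 (none). These points limit the absolute shortfall. They do not supply a reason for the second adjustment.

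Finally, unadjusted pairwise intervals are not simultaneous, whereas Tukey intervals are. That is a real cost, though a small one: section 4.14 promises 95% intervals, not simultaneous ones.

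**Conclusion.** The point holds as an inexpensive improvement, not as an error. Because the global gate is already in 4.8, unadjusted 5% pairwise tests behind it reject whenever the planned rule does, sometimes reject when it does not, and keep the familywise error at 5%. The gain at 216 per group and 0.3 SD is 2.7 points in the plan's own sizing scenario. It is 7.3 points for a given pair, and 13.2 for LNS against both arms, when LNS stands apart. These figures assume equal groups, no covariate adjustment and the stated positions of the third mean. Even the closed test gives 79.4% in the sizing scenario, so the change does not turn the 80% into a pairwise figure.

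A reader might also infer that the SAP already uses unadjusted tests for categorical outcomes. It names CONTRAST statements and is silent on adjustment. The fair conclusion is that the rule is unstated there, so that length-for-age z-score and stunting at 18 months could be judged by different pairwise rules.

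**What to change.** **Section 4.8.** After a significant global test at 5%, make the three pairwise comparisons of continuous outcomes with unadjusted two-sided 5% tests from the ANCOVA model, in place of Tukey-Kramer. State that familywise error is controlled because the procedure is closed with three groups. State the same gated, unadjusted rule for the CONTRAST tests of categorical outcomes. The Scheffé contrasts can stay as they are.

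**Tables.** Note that the pairwise confidence intervals are not simultaneous.

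**Section 3.1.** Say that the 80% refers to the global three-group test with the third mean midway. Give the pairwise power at 216 per group without covariates: about 79% with the closed test, about 77% if Tukey-Kramer is kept. Add that covariate adjustment, or lower loss at birth, would raise it. This sentence is worth adding even if Tukey-Kramer stays.

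**Cost.** Wording only; no change in sample size or data collection. The SAP states that it was written before any knowledge of results, so a change made while that is still true carries no risk of choosing the rule by its outcome. The one loss is simultaneous coverage of the pairwise intervals.
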